2.6.2.3 Analysis of number of days alive out of the hospital

The duration in days of hospital-free survival within 1 year from randomization will be summarized by treatment group, and descriptive statistics (N, mean, standard deviation, median, and quartiles) will be provided. The mean difference between treatment groups will be compared using linear regression model with treatment as fixed factor adjusted for country. The estimated within treatment means, between-treatment difference and 95% confidence interval will be provided for FAS.

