#### **12.5.1.5 Analysis of the number of days alive out of the hospital**

The duration in days of hospital-free survival will be summarized by treatment group, and descriptive statistics (n, mean, standard deviation, median, max, and min) will be provided. The mean difference between treatment groups will be compared using ANCOVA model with treatment and follow-up time. The estimated within treatment means, between-treatment different and 95% CI will be provided for FAS.

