2.1 Data analysis general information

Statistical analyses will be performed by BCRI statistician using R software (version 4.4.1). The blinding of the randomized treatments will be maintained for the clinical trial team until the database has been locked and released for statistical analysis. An independent statistician will be performing the interim analysis of unblinded data for the DSMB meetings.

Summary statistics will be provided by treatment arm for the variables considered in the study. Continuous variables will be summarized using n, mean or median, minimum, maximum, standard deviation or interquartile range. Categorical variables will be summarized using absolute and relative frequency.

Analysis will be performed after data lock when at least 302 participants with events have occurred (CV death or first hospitalization for HF) and when all patients have a minimum follow up of 12 weeks or if a recommendation is made by the Data Monitoring Committee (DMC) to prematurely stop the study.

Data from all sites will be analyzed together with treatment as fixed-effect factor and stratified by country.

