2.6 Analysis of secondary efficacy objectives

2.6.1 Secondary endpoints

The secondary efficacy endpoints besides the primary decomposition as described above are:

1. Time from randomization to the occurrence of the first HF hospitalization or CV death;
2. Time from randomization to all-cause mortality.
3. Time from randomization to sudden death or resuscitated sudden cardiac arrest.
4. Number of visits to an ER due to HF that needs intravenous drugs.
5. Number of days alive out of the hospital within 1 year from randomization.
6. Recurrent events: number of HF hospitalizations and CV deaths.

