2.6.2.5 Handling of missing values/censoring/discontinuations

Patients will be censored for the secondary endpoints according to the same method described in section 2.5.2.1 and 2.5.2.2.

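### The one-year days-alive-out-of-hospital analysis has no usable rule for participants alive but observed for less than 365 days; counted to last observation, a day-90 withdrawal scores the same as a day-90 death

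*SAP*

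**What the plan says.** SAP 2.6.1 lists the endpoint as "Number of days alive out of the hospital within 1 year from randomization". SAP 2.6.2.3 begins with the summary: "The duration in days of hospital-free survival within 1 year from randomization will be summarized by treatment group". It then gives the analysis: "The mean difference between treatment groups will be compared using linear regression model with treatment as fixed factor adjusted for country", with results for the FAS. It has no follow-up term, offset or weight, and does not say how a participant without a full year of observation is scored.

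SAP 2.6.2.5 is the only handling rule for secondary endpoints: "Patients will be censored for the secondary endpoints according to the same method described in section 2.5.2.1 and 2.5.2.2". Section 2.5.2.1 censors at non-CV death, consent withdrawal or last visit; 2.5.2.2 censors at any death, consent withdrawal or last visit.

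Protocol 12.5.1.5 set no window and used a different model: "The mean difference between treatment groups will be compared using ANCOVA model with treatment and follow-up time". SAP section 3 declares the new one-year window. It does not mention that follow-up time left the model and country entered it.

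Three other statements bear on the point:

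- Protocol 9.1.2 treats data after consent withdrawal as missing.
- SAP 2.1 guarantees follow-up only to the extent that analysis occurs "when all patients have a minimum follow up of 12 weeks".
- SAP 2.11 assumed no loss to follow-up.

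**The concern.** A censoring date is information for a survival model. In a linear regression on a day count it can act only as the point where counting stops, and the truncated count is then read as the full-year value. In the 2.5.2.2 list, death and withdrawal are both simply end dates, so nothing separates them: days known to be lost to death and days that were merely unobserved both lower the score.

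Treatment is open-label, so withdrawal could differ between arms. The estimate would then partly measure retention. The gap is particular to this endpoint. The SAP deals with incomplete observation elsewhere: a log follow-up offset for ER visits (2.6.2.2), ties for missing Week 12 NT-proBNP (2.5.2.3), and no imputation for missing MRI values (2.13.2.3).

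**Working it through.** **Inputs from SAP 2.11.** Annual composite rates 0.20 (enalapril) and 0.16 (sacubitril/valsartan); about 66% of first events are HF hospitalizations; uniform 18-month accrual; 36-month study; 450 per arm (SAP 1.1).

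**Assumptions.** The remaining 34% is used as the CV-death hazard. Withdrawal rates and hospital stay lengths are not in the documents.

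**1. The plan's own figure.** The plan gives no expected value for this endpoint, so the check is on its event count. With exponential hazards L, expected events per arm = 450 × [1 − (exp(−1.5L) − exp(−3L)) / (1.5L)].
- L = 0.20: 162.0
- L = 0.16: 135.3
- Total 297.3 against the stated 302 (1.6% low). The rates are therefore read as the plan reads them.

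**2. Expected year-1 effect.** CV-death hazards are 0.34 × 0.20 = 0.068 and 0.34 × 0.16 = 0.0544. Days lost to CV death in year 1 = 365 × [1 − (1 − exp(−L)) / L].
- Enalapril: 12.1 days
- Sacubitril/valsartan: 9.8 days
- Difference: 2.4 days before rounding (3.4 if half of events are CV deaths)

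The HF hospitalization rates are 0.66 × 0.20 = 0.132 and 0.66 × 0.16 = 0.1056, a difference of 0.0264 per year. With assumed stays of 7 to 14 days this adds 0.0264 × 7 = 0.2 to 0.0264 × 14 = 0.4 days, giving about 2.6 to 2.8 in all.

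**3. Scores at day 90 (no hospital days).**

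| Participant | Count to last observation | True one-year value |
|---|---|---|
| Dies at day 90 | 90 | 90 |
| Withdraws alive at day 90 | 90 | between 90 and 365 |

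Up to 365 − 90 = 275 days are unobserved for the second participant.

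**4. Bias from unequal withdrawal.** Shift = imbalance × missing days.
- One percentage point, all at day 90: 0.01 × 275 = up to 2.75 days
- One percentage point, spread evenly over the year: 0.01 × 365 / 2 = 1.8 days

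**5. Simulation.** 200,000 per arm, CV death only, withdrawal at day 90 and independent of outcome, days counted to withdrawal:

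| Withdrawal, enalapril v sacubitril/valsartan | True difference | Estimated difference |
|---|---|---|
| 3% v 3% | 2.3 | 2.2 |
| 5% v 3% | 2.4 | 7.3 |
| 3% v 5% | 2.4 | −3.0 |

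**6. Would the protocol's model have helped?** If follow-up time means observed time, both participants in step 3 have outcome 90 and covariate 90, so the model cannot separate them. With no hospital days simulated, outcome and covariate coincide and the estimated treatment effect is 0 in every scenario: the adjustment removes the mortality effect, because death shortens the covariate.

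**The case against.** The strongest reply is that SAP 2.6.2.3 does not say withdrawals score as deaths. It is silent, and excluding, prorating or imputing is not ruled out. That stands: a reader might infer that the plan states this scoring, and it does not. But 2.6.2.5 is the only rule supplied. Read literally it stops the count at the censoring date, and exclusion sits poorly with an analysis for the FAS.

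A reader might also infer that dropping the protocol's follow-up term created the problem. The documents do not support that. The term is undefined, and as observed time it fails in the same way (step 6).

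A third tempting reading is that the 12-week minimum would truncate many participants. Planned individual follow-up is 18 to 36 months, so under the plan everyone's potential follow-up exceeds one year. The window is a reasonable choice and it is declared. What remains is withdrawal and loss to follow-up.

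The protocol also limits these. Stopping study drug is not withdrawal, reduced or telephone follow-up is offered (3.2.2, 9.1.1), and due diligence is required before a participant counts as lost (9.1.3). This may keep the numbers small, but it does not supply a scoring rule.

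**Conclusion.** The problem is real but narrow. The stated model and the stated handling rule do not fit together, and applying them literally biases the estimate when early withdrawal differs between arms. The expected CV-death effect is about 2.4 days; an imbalance of one point at day 90 can match it, and two points can triple the estimate or reverse its sign. If withdrawal is similar in both arms, the bias is small.

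These sizes depend on the 34% CV-death share and on assumed withdrawal rates and timing. The share omits non-CV deaths and CV deaths that follow an HF hospitalization. The endpoint is secondary; the primary test and the sample size are unaffected.

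**What to change.** In SAP 2.6.2.3, replace the reference to the 2.6.2.5 censoring rule for this endpoint with an explicit rule:

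- Count days after death as zero up to day 365, so that a death gives a complete one-year value.
- For participants alive but observed for less than 365 days, either apply inverse-probability-of-censoring weights, or use days alive out of hospital divided by observed days, scaled to 365, in the same regression.
- Report by arm the number censored alive before day 365.
- List in SAP section 3 that follow-up time was removed from the model and country added.

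Both methods assume that censoring is non-informative given the model. Scaling also assumes the observed rate continues, so it ignores deaths after censoring. That cost is small: at the enalapril CV-death hazard, someone alive at day 90 loses on average 365 × [0.753 − (1 − exp(−0.068 × 0.753)) / 0.068] = 6.9 of the remaining 275 days. Scaling therefore overstates the score by about 7 days, where counting to withdrawal understates it by about 268.

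The cost is SAP wording and a little programming, with no new data. The rule should be settled before treatment codes are released for analysis.

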2.6.2.4 Analysis of recurrent events (CV death and HF Hospitalizations)

Recurrent events will be examined by using 2 methods. Initially, the semiparametric proportional-rates model described by Lin et al. (2000) – Lin, Wei, Yang, and Ying (LWYY). This is an extension of the proportional-hazards model and is based on the gap-time approach that considers the times since the previous event, that is, the interevent time. The LWYY model uses robust standard errors to account for the interdependence of events within an individual. Results will be presented in Rate Ratios with 95% confidence intervals and the recurrent events within each group will

be presented with incidence per 100-patient year. The second statistical method will be the joint frailty model, in that case a treatment rate ratio will be presented by each outcome separately (CV deaths and HF Hospitalizations).

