2.13.2.3 Statistical hypothesis, model, and method of analysis

Summary statistics by treatment arm will be presented for each MRI measurement. Evaluations of all MRI measurement at 8-month will be performed adjusted for baseline values. The reduction of fibrosis and the improvement of cardiac structure after 8 months of treatment will be analyzed using generalized mixed linear models considering the hierarchical effect of study site and participant. Results will be graphically displayed in boxplots. Missing values will not be imputed; analyses will be performed on FAS populations, including only participants with available MRI data.

3 Change to protocol specified analyses

SAP second version includes the recurrent event as a key secondary endpoint, changed the number of days alive out of the hospital time definition changed to within 1 year from randomization, and the NT-ProBNP evaluation at month 8 was included as exploratory endpoint.

4 Appendix

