$$\psi = \frac{\sum_{i=1}^4 w^{(i)} n_{Sacubitril}^{(i)}}{\sum_{i=1}^4 w^{(i)} n_{Enalapril}^{(i)}}$$

To compute the bootstrap:

1. **Resampling:** Perform resampling of the patients with replacement, maintaining the original number of patients per group in each stratum **M** times. ($M \geq 10,000$)
2. **Match Evaluation:** For each resampled stratum, compute match outcomes using **resultados_wr**.
3. **Win Ratio Computation:** Calculate the Win Ratio **M** times for each country.
4. **Dong's Win Ratio Estimation:** Compute the Dong's Win Ratio for all **M** samples using matrix **W** (since stratum sizes remain unchanged), storing results in an auxiliary variable **Strata_results**.
5. **Confidence Interval Calculation:** Compute and return the **95% confidence interval (CI)** for each stratum and the overall Dong's Win Ratio using the **2.5th and 97.5th percentiles** of the **M** resamples.

5 Reference

Bocchi, E. A., Rassi, S., & Guimarães, G. V. (2018). Safety profile and efficacy of ivabradine in heart failure due to Chagas heart disease: a post hoc analysis of the SHIFT trial. *ESC Heart Failure*, 5(3), 249–256. <https://doi.org/10.1002/ehf2.12240>

D. Y. Lin, L. J. Wei, I. Yang, & Z. Ying. (2000). Semiparametric Regression for the Mean and Rate Functions of Recurrent Events. *Journal of the Royal Statistical Society. Series B (Statistical Methodology)*, 62(4), 711–730. <http://www.jstor.org/stable/2680616>

de Diego, C., González-Torres, L., Núñez, J. M., Centurión Inda, R., Martín-Langerwerf, D. A., Sangio, A. D., Chochowski, P., Casasnovas, P., Blazquez, J. C., & Almendral, J. (2018). Effects of angiotensin-neprilysin inhibition compared to angiotensin inhibition on ventricular arrhythmias in reduced ejection fraction patients under continuous remote monitoring of implantable defibrillator devices. *Heart Rhythm*, 15(3), 395–402. <https://doi.org/10.1016/j.hrthm.2017.11.012>

Grambsch P, Therneau T (1994), Proportional hazards tests and diagnostics based on weighted residuals. *Biometrika*, 81: 515-26.

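### The SAP names the LWYY rate model for recurrent events but describes it as a gap-time model; the time scale should be stated as time since randomisation

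*SAP*

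**What the plan says.** SAP section 2.6.1 lists as its sixth secondary endpoint "Recurrent events: number of HF hospitalizations and CV deaths". Section 2.6.2.4 gives the analysis. The first method is "the semiparametric proportional-rates model described by" a 2000 paper listed in the SAP references under the title "Semiparametric Regression for the Mean and Rate Functions of Recurrent Events". The next sentence calls it an extension of the proportional-hazards model that "is based on the gap-time approach that considers the times since the previous event, that is, the interevent time".

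The section continues: "The LWYY model uses robust standard errors to account for the interdependence of events within an individual", and "Results will be presented in Rate Ratios with 95% confidence intervals", beside incidence per 100 patient-years in each group. Then: "The second statistical method will be the joint frailty model", with a separate ratio for each outcome.

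On status, SAP section 3 states: "SAP second version includes the recurrent event as a key secondary endpoint". The version history and section 2.6.1 call it secondary only, and the protocol's list in section 12.5.1 does not contain it. The 2.5% one-sided error control is stated with the primary win ratio (SAP 2.5.2). No testing order is given for secondary endpoints.

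**The concern.** A rate or mean function accumulates from a fixed origin. In LWYY that origin is randomisation, and each participant stays in the risk set until death, withdrawal or end of follow-up, however many events have occurred. A gap-time model restarts the clock at each event. The two share the Cox-type partial likelihood and can carry the same robust standard errors, so the rest of the section does not tell the analyst which to fit.

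Two things are at stake.

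- **The analysis is not determined.** The section would let an analyst defend LWYY on time since randomisation, a pooled gap-time model, or a gap-time model stratified by event order, since it is silent on order. A prespecified analysis should allow one.
- **The estimand changes.** Second and later gaps exist only for participants who have already had an HF hospitalization. If participants differ in underlying risk and treatment lowers the rate, those who reach a second gap on sacubitril/valsartan are on average frailer than those who do so on enalapril. The ratio is then no longer the ratio of event rates since randomisation that the label and the incidence table imply.

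**Working it through.** **Inputs from the documents (SAP 2.11; allocation from SAP 1.1).** 900 participants, 1:1; first-event rates 0.20 (enalapril) and 0.16 per year; 66% of first events are HF hospitalizations; uniform accrual over 18 months; follow-up 18 to 36 months; no loss to follow-up. The enalapril rates are therefore 0.66 × 0.20 = 0.132 per year for HF hospitalization and 0.34 × 0.20 = 0.068 for CV death.

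**Step 1: the plan's own figure.** With exponential times and rate L, P(event) = 1 − [exp(−1.5L) − exp(−3L)] / (1.5L).

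- Enalapril, L = 0.20: 1 − (0.7408 − 0.5488)/0.30 = 0.360; × 450 = 162.0.
- Sacubitril/valsartan, L = 0.16: 1 − (0.7866 − 0.6188)/0.24 = 0.3006; × 450 = 135.3.

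The total is 297.3 against 302 stated, a difference of 1.6%, so the planning inputs are read correctly. The documents give no effect size or power for the recurrent-event endpoint.

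**Step 2: both models on the same data.** Recurrent HF hospitalizations plus CV death were simulated for 900 participants, with CV death counted as an event and ending follow-up. Each dataset was fitted on time since randomisation and on pooled gap time (not stratified by event order), both with clustered robust standard errors. The following are assumptions, not in the documents: gamma frailty with variance 0 to 4, shared with death or not; an HF hospitalization rate multiplied by 1, 3 or 5 for 3 months after each HF hospitalization; and, except in the last row, a ratio of 0.80 for both event types.

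| Scenario | Time since randomisation | Gap time | Crude incidence ratio | Rejection at one-sided 2.5% |
|---|---|---|---|---|
| Variance 2, shared | 0.819 | 0.824 | 0.819 | 29.9% vs 29.7% |
| Variance 4, not shared | 0.798 | 0.803 | 0.798 | 35.1% vs 35.0% |
| Variance 4, shared | 0.833 | 0.838 | 0.832 | 21.0% vs 20.9% |
| Variance 4, shared, rate ×3 after event | 0.814 | 0.824 | 0.814 | 19.6% vs 19.8% |
| Variance 4, shared, rate ×5 after event | 0.796 | 0.809 | 0.795 | 21.9% vs 22.1% |
| No effect, variance 4, shared | 1.000 | 1.000 | 1.000 | 2.4% vs 2.3% |

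Without frailty the two models agree (0.806 and 0.806). The largest shift is 0.809 − 0.796 = 0.013. On the log scale that is (0.228 − 0.212)/0.228 = 7% of the effect. The standard error shrinks with it: 0.228/0.197 = 1.16 and 0.212/0.183 = 1.16, which is why power does not move. Across all scenarios power agreed within 0.7 points. With no treatment effect, rejection was 2.1 to 2.6% for LWYY and 2.1 to 2.5% for gap time.

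LWYY on time since randomisation matches the crude incidence ratio within 0.001 in every row shown. The gap-time estimate does not once there is both frailty and a treatment effect.

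**Step 3: the selection itself.** Runs of 100,000 participants:

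| | Variance 2, not shared | Variance 4, shared |
|---|---|---|
| Mean frailty at start of second gap, sacubitril/valsartan vs enalapril | 2.50 vs 2.43 | 3.34 vs 3.18 |
| LWYY | 0.799 | 0.832 |
| Pooled gap time | 0.803 | 0.838 |
| First gaps only | 0.817 | 0.860 |
| Later gaps only | 0.827 | 0.867 |

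Over all six large runs the frailty imbalance was about 2 to 5%, later gaps held about 18 to 31% of events, and the pooled estimate moved by 0.002 to 0.007. The first-gap ratio is also nearer 1 than LWYY, so not all of the later-gap difference is selection. The pooled estimate sits below both parts because enalapril contributes more of the high-rate later gaps. An order-stratified gap-time model loses that offset and would be expected to move further than the pooled one.

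**The case against.** The strongest reply is that the operative instruction is the named model. The section cites the LWYY paper, asks for robust standard errors and reports rate ratios, and the cited title concerns mean and rate functions. On that view the gap-time clause is a loose description, and a competent programmer would fit standard LWYY. This stands in part: the text does not show that a gap-time model will be fitted. But the clause is the only statement about the time axis, and nothing elsewhere corrects it.

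A reader might go further and infer that the randomised comparison is broken after the first event. The documents and the check do not support that. The first gaps of all randomised participants stay in the pooled model, type I error holds, and the shift is small. Nor would the correction return exactly 0.80: when frailty is shared with CV death, LWYY itself gives 0.819 and 0.833, a larger departure than the gap-time increment. What the correction delivers is a defined quantity that agrees with the reported incidence rates.

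It is also fair to say that this endpoint is outside any stated error control, is called key only in SAP section 3, and is backed by the joint frailty model. These points lower the priority. They do not settle which first model is meant, since the second method gives separate ratios by outcome.

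**Conclusion.** SAP 2.6.2.4 contradicts itself: it names one model and describes another with a different estimand, so the analysis is not determined as written. At the planned event rates the consequence for a pooled estimate is small: no shift without heterogeneity, and about 0.002 to 0.013 toward 1 with frailty variances up to 4, with type I error and power essentially unchanged. Those figures rest on the assumed frailty and post-event rates, which the documents do not give, and on the gap-time model not being stratified by event order. The primary win ratio, the sample size of 900 and the 302-event target do not use this model. It should be fixed because the specification is ambiguous and the reported ratio would be mislabelled. Large bias is not the reason, and the trial's main conclusion does not depend on it.

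**What to change.** In SAP 2.6.2.4, delete the gap-time clause and state: LWYY marginal proportional-rates model on time since randomisation (counting-process start-stop intervals), treatment as covariate, stratified by country, robust sandwich variance clustered on participant. Keep the joint frailty model as the second method.

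Name country explicitly. SAP 2.1 and 2.6.2.1 stratify by country, whereas the SAP describes the randomisation strata in two ways: country plus prior ACEI/ARB use in 2.1.2, and country alone in 2.2. A reference to the randomisation strata would bring in a second ambiguity.

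The cost is one sentence and the time origin in the analysis dataset, settled before the treatment codes are released for analysis. No data collection, sample size or primary analysis changes.
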